VERSION DATE: May 4, 2018

Analysis of Aim 1: ADAPT comparative effectiveness hypotheses will be tested using standard normal theory Analysis of Variance and multiple regression techniques in structural equation modeling (SEM) with a focus on growth curve analyses for follow up data. We will specify analyses to test Hypothesis 1: NGR families in both the ADAPT group-based condition and the ADAPT web-facilitated condition will show greater pre-post improvements in observed parenting, and parent, child, and couple functioning relative to the self-directed web condition; and Hypothesis 2: ADAPT group-based condition will be equally effective as the individualized ADAPT web-facilitated condition.

Analyses for Hypothesis 1 of Aim 1. We will employ standard normal theory pre-post Analysis of Variance and structural equation modeling (SEM) growth curve analyses for the long-term follow up. For the immediate pre-post analyses we will conduct a 3 group by 2 repeated measures Analysis of Variance for parenting, child, and couple functioning constructs focusing on the comparison of change across the Group Based, Individualized Facilitated, and Self-directed ADAPT conditions. The study randomly allocates 360 NGR families across the three conditions ($n = 120$ per group). For the 6-month assessment, we estimate a projected 5% attrition rate and over the 24-month follow up we expect roughly 15% attrition. In two prior PMTO randomized trials with intensive multiple-method family assessments, family retention was 88% and 86%, respectively, at 30-month follow-ups [2, 12]. In both of those studies, there were no differential rates of attrition between intervention and controls, there was less than 5% attrition by the immediate 6 month post-test assessment, and less than 15% attrition by the 24 month assessment. Using an alpha level of .05 and considering 5% attrition over the first 6 months, a pre-post design with 3 groups of 114, within subject $SD = 1$, and between groups $SD = .71$; the study is powered .81 to minimally detect a small group by time interaction effect ($ES = .12$), small time effect ($ES = .15$), and small group effect ($ES = .21$) for given parenting, child, couple or parent constructs.

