Follow Up Analyses. For the intent to treat (ITT) analyses of long term follow up, we will specify latent growth models (LGM) recommended for long term effectiveness designs involving maximum likelihood SEM. LGMs have become more standard because they more reliably assess change. Growth models combine individual and group levels of analysis, taking into account mean growth and individual variation. Fixed effects (e.g., random assignment to ADAPT, parent and child gender) and time-varying random effects may be estimated using chronometric time weights. A model specifying an initial status latent variable (assessing variance in BL differences) and a linear slope latent variable (estimating individual differences in change over time), would be specified using factor weights of 1, 1, 1, 1, for the respective repeated measures, and factor weights of 0, 1, 2, and 4 for growth. The first step in LGM is to

PROTOCOL TITLE: Comparing Web, Group, and Telehealth Formats of a Military Parenting Program

VERSION DATE: May 4, 2018

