identify the model that best characterizes patterns of growth. We can also specify an additional nonlinear quadratic factor, a higher order polynomial function to capture any nonlinearity. Accelerated or decelerated change would be specified with loadings fixed at 0, 1, 4, and 16. A sequential set of models tests the latent variances and model fit across a random intercept, linear growth, and quadratic model to determine the optimal growth pattern. The comparative effectiveness hypothesis for observed parenting is shown in Figure 2 as linear growth. Group Based and Web Facilitated will be contrasted to the Self-Directed omitted group. Analyses will test that the Group Based effect ($\beta_1 > 0$) and the Web Facilitated ($\beta_2 > 0$) will show greater 2-year improvements relative to Self-Directed. For the LGM in Figure 2 we estimated power using Mplus Monte Carlo simulations with 1000 replications. An advantage of this approach is the ability to incorporate specific patterns of expected attrition over time. For the figure in Figure 3, contrasts for Group Based and Web Facilitated were fixed at a mean of .33 and variance of .22 representing the random allocation across groups. The latent initial status intercept and latent growth factors were specified reflecting a commonly observed ratio of 5:1 for the variance components (Initial Status $\psi_2 = .5$ and SD = .70; and Linear Growth $\psi_2 = .1$, SD = .31). The effect size (ES) is then the ratio of group contrast mean differences in the latent growth factor divided by the SD for growth. A sample size of 306 (cumulative attrition of 15% over 2 years, specified as .05, .10 and .15 over time) obtained power of .98 respectively to detect small effects (ES=.10) for β_1 and β_2 relative to Self-Directed and likewise for child, couple, parent adjustment.

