assessments with the target 5-12 year old child, and complete parent-child observational tasks, and adult measures (approximately 100 minutes total). Families who prefer assessment outside the home may go to the local UMN or UM project office.

Note: Child care is offered to families for the siblings that are not participating in the research. In the event that child care staff are not available we will offer families a \$30 gift card stipend to provide their own child care during the in-home assessment.

5. Teachers will be contacted (at each time point) via secure, encrypted email, with an explanation of the study, and a copy of the parent's release of information. They will be directed to the study website to complete questionnaires. Teachers not responding will receive materials by mail, with follow-up calls. Teachers who do not want their compensation may choose to give the gift card back to ADAPT or to MCEC.

6. Following BL assessment, participants are electronically given random assignment to the G, W, or F study conditions, with 120 families assigned to each condition. The group condition will be run in three cohorts, with 2 groups of up to 10 families in each cohort of 20 families (up to 60 families in each of the two sites – i.e. 120 total, considerably more than we estimate will participate). In both online conditions, families may participate as they enter the study. However, given the necessity of running groups in cohorts and the need for equivalence in analysis, we will also assign individuals in the web conditions to a cohort.

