7. Participants in the Group (G) condition will be assigned to a 14-week ADAPT facilitator-led group. Groups will be organized as follows: (a) Orientation. The group facilitator will provide a telephone orientation to the program to: 1) provide program information, 2) address any potential barriers to participation, and/or concerns about group attendance, 3) provide information about features and limits to confidentiality within intervention groups, and 4) direct attention to the ADAPT website and the consent for intervention form. The facilitator will explain information will be confidential except when harm to self or others is expressed, or child maltreatment reporting is mandated. Facilitators will describe the 14 week ADAPT group and the web-enhancement component, will encourage group participation of both parents/ caregivers in the home in 2-caregiver families, and will troubleshoot barriers to group participation. (b) Logistics and locations. Sessions will begin as soon as the group is full. Five to ten families (up to 20 individuals) will participate in each group. Two groups will be offered in each cohort. Groups will be facilitated by trained ADAPT facilitators, all of whom have previously delivered successful ADAPT or PMTO groups for mothers and fathers with high retention and satisfaction. We are currently training a cohort of VA therapists, and Michigan community mental health professionals in ADAPT, and these individuals will join our current ADAPT facilitator team of 14 individuals based in MN. The 14 week ADAPT group interventions will take

PROTOCOL TITLE: Comparing Web, Group, and Telehealth Formats of a Military Parenting Program

VERSION DATE: May 4, 2018

place at community locations in the Detroit, Ann Arbor, Twin Cities, and Duluth areas, convenient to participants. We have selected community locations (e.g., schools, libraries) rather than VA or Armories to reduce concerns about the stigma of services, to normalize the ADAPT groups as health promotion, and to ensure proximity to homes.

8. Participants assigned to the web-only (W)/self-directed condition will be instructed to log in to the ADAPT website. The website will offer a short (10 minute) introduction to the program, as well as an informed consent form to participate. Then, participants will be given access to the ADAPT dashboard (program content list) and instructions on going through the components.

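### Arm G is taught in up to about 12 parenting groups, but the stated Hypothesis 1 tests and power treat families as independent; if change correlates within groups, alpha for contrasts with arm G exceeds .05

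*Protocol*

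**What the plan says.** Families are randomised individually, 120 per arm. In the group arm, "Participants in the Group (G) condition will be assigned to a 14-week ADAPT facilitator-led group" (Protocol 5.2, item 7), and "Five to ten families (up to 20 individuals) will participate in each group". Item 6 gives the layout: "The group condition will be run in three cohorts, with 2 groups of up to 10 families in each cohort of 20 families", at each of two sites. The same item describes the capacity as "120 total, considerably more than we estimate will participate". Self-directed families have no live facilitator, and web-facilitated families meet a facilitator one family at a time (4.1). Only arm G is therefore nested in parenting groups.

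For the pre-post test of Hypothesis 1, "we will conduct a 3 group by 2 repeated measures Analysis of Variance" (1.1, repeated in 17.1). Longer follow-up uses a maximum likelihood latent growth model with contrasts of Group and Web-Facilitated against Self-Directed. Hypothesis 2 compares Group with Web-Facilitated by a test described both as one-sided non-inferiority and as two one-sided tests. The power inputs are family counts: "considering 5% attrition over the first 6 months, a pre-post design with 3 groups of 114" for the pre-post test, "A sample size of 306 (cumulative attrition of 15% over 2 years" for the growth model, and two groups of 102 for Hypothesis 2. The pre-post calculation claims power of .81 for a group-by-time effect size of .12. None of these statements includes a parenting-group term, a cluster-robust variance, an ICC or a design effect.

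**The concern.** Families who share facilitators, peers and 14 weekly two-hour sessions may change together. Individual randomisation does not prevent this, because the correlation arises during delivery. When it is present, the mean of arm G varies more than the same number of independent families would imply. A test that ignores it then uses a standard error that is too small for any contrast with arm G. Group versus Self-Directed is half of Hypothesis 1, so the error falls on a main comparison.

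Two phrases in the Protocol could be taken to cover this, and neither does. "Growth models combine individual and group levels of analysis, taking into account mean growth and individual variation" (1.1) defines its own levels as mean growth and individual variation, not parenting groups. The cohort label given to web families (5.2, item 6) does not separate the two groups within a cohort and site, and no stated model term uses it.

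**Working it through.** **Number of groups.** 3 cohorts × 2 groups × 2 sites = 12 (5.2, item 6). With 114 families analysed, m = 114/12 = 9.5 per group; with 102, m = 8.5.

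**The plan's own figure.** For the group-by-time F test with independent families, the noncentrality is 2 × 342 × .12² = 9.85 on 2 and 339 df. Power is .806 against the stated .81, so the stated figure contains no design effect.

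**Assumptions.** The ICC of change is not in the documents; the range .01 to .10 is assumed. Attendance is not given either, so three scenarios are shown: near-full groups (m = 9.5), half of arm G attending in groups of 5, and half attending in groups of 10.

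**Alpha of the uncorrected contrast, G versus a web arm.** DEFF = 1 + (m − 1) × ICC. With equal arms, the true variance divided by the assumed variance is R = (DEFF + 1)/2. If half attend and the rest are uncorrelated, R = (DEFF + 3)/4. Two-sided alpha = 2[1 − Φ(1.96/√R)]. For example, m = 9.5 and ICC .05 give DEFF = 1.425, R = 1.213 and alpha = .075.

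| ICC | Near-full, m = 9.5: R | alpha | Half, m = 5: R | alpha | Half, m = 10: R | alpha |
|---|---|---|---|---|---|---|
| .01 | 1.043 | .055 | 1.010 | .051 | 1.023 | .053 |
| .02 | 1.085 | .060 | 1.020 | .052 | 1.045 | .055 |
| .05 | 1.213 | .075 | 1.050 | .056 | 1.113 | .063 |
| .10 | 1.425 | .101 | 1.100 | .062 | 1.225 | .077 |

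Simulating the stated three-arm F test on change (60,000 replications) gives .054/.058/.075/.099 near-full, .050/.052/.055/.062 for half in groups of 5, and .052/.055/.062/.077 for half in groups of 10. At 102 families per arm, with all attending, the contrast has alpha .054/.059/.072/.095.

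**Power.** The .81 belongs to the three-arm F test, so the G contrast needs its own baseline. Assume Group and Web-Facilitated are equally better than Self-Directed by d SDs of change. The noncentrality is then 114 × (2/3)d² = 76d², and 76d² = 9.85 gives d = .36. For Group versus Self-Directed under independence, .36 × √(114/2) = 2.718 and power is Φ(2.718 − 1.960) = Φ(.758) = .776.

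- Uncorrected contrast, near-full groups: Φ(.758/√R).
- Cluster-aware contrast: noncentral t with Satterthwaite df, using 11 df for the 12 group means.
- Uncorrected three-arm F test: simulated (40,000 replications).

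| ICC | Uncorrected G contrast | Cluster-aware G contrast | Uncorrected three-arm F |
|---|---|---|---|
| 0 | .776 | .756 | .803 |
| .01 | .771 | .737 | .803 |
| .02 | .767 | .718 | .810 |
| .05 | .754 | .666 | .805 |
| .10 | .737 | .591 | .811 |

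About 2 points of the cluster-aware loss (.776 to .756) come from the small number of clusters alone.

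**Hypothesis 2, 102 per arm, m = 8.5, all attending.** R = 1.038/1.075/1.188/1.375. On the one-sided non-inferiority reading, error at the margin is 1 − Φ(1.645/√R) = .053/.056/.066/.080. On the two one-sided tests reading, k = .25/√(2/102) = 1.785, and error at the margin is Φ(−1.645/√R) − Φ((1.645 − 2k)/√R) = .024/.025/.027/.030.

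**The case against.** The strongest reply is that this is detail for an analysis plan. The Protocol never says that families are independent or that group membership will be ignored. It names families of models, and a random effect or robust variance is commonly specified later. Section 5.2 already ties web families to cohorts for the analysis, and section 1.1 plans moderator analyses of dosage, participation and fidelity. This is fair as far as it goes, and a later plan could add the term. The point stands because the Protocol names its tests and fixes its power basis, and the .81 is demonstrably the independent-families figure. Adding a term later would leave that statement too favourable for contrasts with arm G.

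The second reply is about size, and it stands. No passage supports any particular ICC, and the largest alphas need near-full groups, which section 5.2 itself does not expect. With half attending and an ICC of .01 to .02, alpha is only .051 to .055.

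Three stronger readings are tempting, and the documents do not support them:

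- A reader might infer that the stated tests lose much power. They do not: inflated alpha keeps the F test near .81, and the uncorrected contrast falls by about 4 points at most (.776 to .737). The larger loss belongs to a test that accounts for clustering.
- A reader might infer that Hypothesis 2 is inflated in the same way. On the two one-sided tests reading, its error stays below .05.
- A reader might infer that group membership goes unrecorded. Nothing says so: families are assigned to groups, and weekly attendance is analysed (17.1).

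**Conclusion.** The concern holds conditionally and should be corrected. As written, the Hypothesis 1 tests give standard errors that are too small for Group versus Self-Directed whenever the ICC of change within parenting groups is above zero. Over assumed ICCs of .01 to .10, alpha lies between about .051 and .101. The upper end requires both a high ICC and near-full groups; with an ICC near zero or poor attendance the effect is slight. The three-arm F test behaves similarly.

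The power consequence is that a valid Group versus Self-Directed test with near-full groups has about .74 to .59, against .78 under independence. This rests on an effect of .36 SD of change, derived from the plan's effect size by assuming that Group and Web-Facilitated perform alike. Hypothesis 2 is affected above .05 only on the one-sided reading (.053 to .080 with all attending). The contrast between the two web arms is not affected by parenting groups.

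**What to change.** For the pre-post, growth and Hypothesis 2 analyses that involve arm G, specify either a partially nested model (random parenting-group effect in arm G only) or a cluster-robust variance. Use a small-sample correction suited to about 12 clusters. Define nesting by assigned group, and add a sensitivity analysis that treats never-attenders differently. Carry the parenting-group identifier into the analysis data. Restate power for contrasts with arm G, using the cluster-aware test, over ICC .01 to .10 and groups of 5 to 10, with an allowance for non-attendance.

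The cost is analysis wording, one variable in the analysis file and a recomputed power statement. Intervals for arm G contrasts will be somewhat wider, the group variance will rest on few degrees of freedom, and the stated power will be less favourable.

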PROTOCOL TITLE: Comparing Web, Group, and Telehealth Formats of a Military Parenting Program

VERSION DATE: May 4, 2018

be completed during the baseline or follow-up, or study staff will provide funds for the family to travel to a local library, University, etc. to gain computer access.

Sources of Materials

- Research material obtained from human subjects will consist of data collected specifically for this study.

The data will include:

1. Web-based questionnaires filled out by families
2. Observational coding data based on videotaped parent-child interaction tasks completed by families
3. Short questionnaire packets filled out by families and teachers
4. Short surveys and web conference calls completed by expert panel members.
5. Audio and video tape of parent's response to KidVid (video of parenting tasks)

Measures and Assessments:

There are 4 assessments: Time 1- baseline (BL, prior to start of the intervention), Time 2 - six months post BL (post-intervention, given 4-5 month intervention at 3 sessions/month, allowing for holidays, etc), Time 3- 12 months following BL, and Time 4, 24 months after BL. Assessments are weighted to be gathered in the first year, (BL, 6, and 12 months) to gauge intervention effects immediately at posttest (i.e., T2) and at T3, which is when parenting and teacher report outcomes indicated change in prior studies. All measures (i.e., child, parent, and teacher report, and direct observations) will be gathered annually (T1, T3, T4), ensuring that teachers are different at each assessment. At T2, only parent report data will be gathered, online, (no in-home assessment) to minimize participant burden in Year 1, and because in prior studies observed parenting and teacher report outcomes indicated change at 12 months, while parent report indicated some change immediately posttest. Child self-report measures will be gathered (and were standardized with) children over age 8. Measures are summarized below:

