Some Smart Phone Application users may be asked to participate in a short interview (via phone or email) about their use of the App to help improve it for other users and for the development of other versions of the App (i.e. for I-phones). The purpose of the interview is for program improvement only. This would be a one-time phone call lasting no more than 10-15 minutes with study participants who have used the App during the course of the study. Participants

PROTOCOL TITLE: Comparing Web, Group, and Telehealth Formats of a Military

Parenting Program

VERSION DATE: May 4, 2018

will be emailed first to ask if they would be willing to answer some questions and when is a good time to call. Participants who are interested, but do not have time for a call, may be emailed the questions and asked to respond in that manner.

Study participants will be given a \$5 gift card for their one time participation in this interview. The goal would be to obtain feedback from at least 10 study participants. Note: See list of interview questions.

5.3 Follow-Up:

There are 4 assessments: Time 1- baseline (BL, prior to start of the intervention), Time 2 - six months post BL (post-intervention, given 4-5 month intervention at 3 sessions/month, allowing for holidays, etc), Time 3- 12 months following BL, and Time 4, 24 months after BL. Assessments are weighted to be gathered in the first year, (BL, 6, and 12 months) to gauge intervention effects immediately at posttest (i.e., T2) and at T3, which is when parenting and teacher report outcomes indicated change in prior studies. All measures (i.e., child, parent, and teacher report, and direct observations) will be gathered annually (T1, T3, T4), ensuring that teachers are different at each assessment. At T2, only parent report data will be gathered, online, (no in-home assessment) to minimize participant burden in Year 1, and because in prior studies observed parenting and teacher report outcomes indicated change at 12 months, while parent report indicated some change immediately posttest. Child self-report measures will be gathered (and were standardized with) children over age 8.

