26.0 References

ADAPT4U MEASURES

KEY:

OL = Collected online prior to the interview

IH = Collected during the in-home interview

	Items	T1		T2		T3		T4	
		OL	IH	OL	IH	OL	IH	OL	IH
Measures - Parents									
Demographics (vary slightly by time point)		x		x	N/A	x		x	
Dyadic Adjustment Scale (DAS-7)	7	x		x	N/A	x		x	
Five Facet Mindfulness Questionnaire (FFMQ)	39	x		x	N/A	x		x	
The Alcohol Use Disorders Identification Test (AUDIT)	10	x		x	N/A	x		x	
Difficulties in Emotion Regulation Scale (DERS)	36	x		x	N/A	x		x	
Center for Epidemiologic Studies Depression Scale (CES-D)	20	x		x	N/A	x		x	
ODS Interpersonal Support Evaluation List (ISEL)	16	x		x	N/A	x		x	
Life Events Checklist (LEC-5)	17	x			N/A			x	
The List of Threatening Experiences (LTE)	12	x			N/A	x		x	
Military Organization ([name]'s Questions)	6	x		x	N/A	x		x	
Child Lifetime Events	19							x	
Deployment Risk and Resilience Inventory – 2 (DRRI-2) Section K (number of questions dependent on exposure to military context and deployment)	16-64							x	
PTSD Checklist - Military (PCL-M) (parents who were deployed/mobilized in support of GWOT)	18		x	x	N/A		x		x
PTSD Checklist – Civilian (PCL-C) – (parents who were not deployed/mobilized in support of GWOT)	17		x	x	N/A		x		x
Deployment Risk and Resilience Inventory (DRRI) – Sections I & J (Deployed Parent Only)	30		x		N/A		x		x
Deployment Risk and Resilience Inventory – 2 (DRRI-2) – Items 1, 2, 5, 6 from Section I (parents who were deployed/mobilized in support of GWOT)	4		x		N/A		x		x
Behavioral Assessment System for Children – 2 (BASC) PRS-P (parents of children age 5)	134		x	x	N/A		x		x
Behavioral Assessment System for Children – 2 (BASC) PRS-C (parents of children ages 6-11)	160		x	x	N/A		x		x
Behavioral Assessment System for Children – 2 (BASC) PRS-A (parents of children 12 and older)	150		x	x	N/A		x		x
Alabama Parenting Questionnaire – short (APQ)	9		x	x			x		x
Coping with Children's Negative Emotions Scale (CCNES)	72		x	x	N/A		x		x
Parent Locus of Control – short (PLOC)	24		x	x	N/A		x		x
Wechsler Abbreviated Scale of Intelligence – 2 (WASI-2) – vocabulary and matrix reasoning only	61		x		N/A				
Operation Span Task (OSPART) – working memory	N/A		x		N/A		x		x
Family Interaction Tasks	N/A		x		N/A		x		x

PROTOCOL TITLE: Comparing Web, Group, and Telehealth Formats of a Military Parenting Program
 VERSION DATE: May 4, 2018

	Items	T1		T2		T3		T4	
		OL	IH	OL	IH	OL	IH	OL	IH
Measures - Child									

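### The 6-month pre-post ANOVA and its .81 power cannot apply to observed, teacher-report or child-report outcomes, because only parent report is collected at that visit

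*Protocol*

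**What the plan says.** Protocol 1.1 (Analysis of Aim 1) states Hypothesis 1 as "greater pre-post improvements in observed parenting, and parent, child, and couple functioning relative to the self-directed web condition". For the immediate pre-post test it plans a 3 x 2 repeated measures ANOVA. It reports power of .81 for a group-by-time ES of .12, "considering 5% attrition over the first 6 months, a pre-post design with 3 groups of 114", for parenting, child, couple and parent constructs alike. Sections 17.1 and 17.2 repeat the test and the figure. None of these places restricts either by informant.

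Section 5.2 (Measures and Assessments) identifies the post-test: assessments are timed "to gauge intervention effects immediately at posttest (i.e., T2) and at T3", T2 being six months after baseline. It then limits that visit: "At T2, only parent report data will be gathered, online, (no in-home assessment". For everything else, sections 5.2 and 5.3 say "All measures (i.e., child, parent, and teacher report, and direct observations) will be gathered annually (T1, T3, T4". The ADAPT4U Measures table agrees: the row for "Family Interaction Tasks" is not applicable at T2, and no child or teacher measure is collected then. The stated reasons are participant burden and that "in prior studies observed parenting and teacher report outcomes indicated change at 12 months".

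For long-term follow-up, section 1.1 gives observed parenting a linear latent growth model, written for four waves with loadings 0, 1, 2, 4 and attrition .05, .10, .15. A quadratic factor is optional.

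**The concern.** The protocol fixes a test, a time point and a power figure together, and the visit schedule supplies no data for that combination in three of the four data sources. One of them, direct observation, is the outcome that Hypothesis 1 names first.

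Two consequences follow. First, the analyst must later decide whether pre-post for observed parenting means 12 months, 24 months or the growth slope alone, and that choice should not be open once data are in hand. Second, a reader will credit .81 to outcomes that it does not cover. For teacher and child report the overstatement could be larger than for observation, because their numbers also depend on teacher response and on the child's age.

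**Working it through.** **Inputs from the protocol.** 120 families per arm; attrition .05, .10, .15 at 6, 12 and 24 months; alpha .05; within-subject SD 1; group-by-time ES .12; stated power .81.

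**Which visit the .81 belongs to.** 120 x .95 = 114, so the power statement is for T2. At 12 months 120 x .90 = 108, and at 24 months 120 x .85 = 102.

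**Reproducing the .81.** Group-by-time F test with df 2 and 3n - 3, noncentrality 3n x 2 x ES² / SD².
- n = 114: 342 x 2 x .0144 = 9.85; power .806. The stated .81 reproduces.

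**Same test, baseline to 12 months.**
- n = 108: 324 x 2 x .0144 = 9.33; power .782. ES detectable with .81 power: .124, against .121 at 114 per arm.
- This carries the 6-month SD of 1 over to an interval twice as long. With the raw effect unchanged, SD 1.1 gives 9.33 / 1.21 = 7.71 and power .70; SD 1.2 gives 9.33 / 1.44 = 6.48 and power .62. These two SDs are assumptions, chosen to show sensitivity.

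**What is available at T2, by source.**

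| Source | T1 | T2 | T3 | T4 |
|---|---|---|---|---|
| Parent report (e.g. APQ, parent BASC-2, DAS-7, CES-D) | yes | yes | yes | yes |
| Observation | yes | no | yes | yes |
| Teacher report | yes | no | yes | yes |
| Child report | yes | no | yes | yes |

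**The growth model with three waves.** Dropping T2 leaves loadings 0, 2, 4 and attrition .10, .15. Three waves give 3 means + 6 variances and covariances = 9 moments. Identification was checked by the rank of the Jacobian of these moments.
- Linear, random intercept and slope, free residuals: 8 parameters, rank 8. Identified.
- Quadratic with free variance and covariances: 12 parameters (10 with equal residuals), rank 9. Not identified.
- Quadratic mean with zero variance: 9 parameters, rank 9. Identified.
- At four waves (14 moments) the free-variance quadratic has 13 parameters, or 10 with equal residuals, and full rank, so the difficulty arises only for the three-wave sources.

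**Cost to the slope contrast.** With the protocol's intercept variance .5 and slope variance .1, an assumed covariance of 0, and assumed residual variances from .1 to 1.0, the standard error of the slope contrast is 1.5% to 2.2% larger with three waves than with four.

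**Teacher and child numbers.** The protocol gives no expected teacher response. For children, section 5.2 says "Child self-report measures will be gathered (and were standardized with) children over age 8", while section 9.1 admits ages 5-12. The Measures table schedules child BASC-2 forms from age 5, loneliness and friends measures from age 4, and the depression inventory from age 7; only the substance-use survey starts at 10. Section 5.2 and the table conflict, so no single n can be derived.

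**The case against.** The strongest reply is that nothing is untestable. Section 1.1 calls the 6-, 12- and 24-month assessments all post-intervention, so pre-post in Hypothesis 1 need not mean T2. Hypothesis 1 is assigned to growth curves as well as to the ANOVA, and observed parenting is expressly given to the growth model. The ANOVA sentence speaks of constructs, and each domain has a parent-report measure at T2. Leaving observation out at T2 was deliberate and is explained. Details by instrument may sit in a statistical analysis plan that is not shown.

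Much of this stands. It rules out two inferences that a reader might draw. One is that Hypothesis 1 cannot be tested for observed parenting; the linear growth test does so and loses almost nothing with three waves. The other is that the .81 is miscalculated; it reproduces.

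The reply does not remove the fault. The ANOVA is described as immediate, is sized at 6-month attrition, and section 5.2 equates post-test with T2. Its power claim covers all constructs without limit by informant, under a hypothesis that says observed. The reasons given for skipping T2 were never carried into the hypothesis, the test or the power text. This is a stated mismatch within the protocol, not a detail left for later.

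Two further readings are tempting and are not supported. One is that child self-report loses about half its sample to an over-age-8 rule; that follows section 5.2 and ignores the Measures table. The other is that three waves rule out any curvature; only a quadratic factor with free variance is excluded.

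**Conclusion.** The concern holds as an error of scope. The 6-month ANOVA and its .81 are valid for parent-report outcomes and cannot apply to observed, teacher-report or child-report outcomes.

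For observed parenting the loss is small: about .78 instead of .81 at ES .12 when the comparison moves to 12 months. This rests on the protocol's 10% attrition and on an unchanged within-subject SD; a larger SD would cost more than the attrition does. For teacher and child report neither .81 nor .78 can be carried over, and the protocol does not support any replacement figure. It should be corrected, but it does not threaten the design.

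**What to change.** 1. In sections 1.1, 17.1 and 17.2, limit the 6-month ANOVA and its .81 to parent-report outcomes.
2. Name baseline to 12 months (T1 to T3) as the first pre-post comparison for observed, teacher-report and child-report outcomes, and align the wording of Hypothesis 1.
3. State that the growth model for these sources uses three waves (loadings 0, 2, 4; attrition .10, .15), without a quadratic factor of free variance. A quadratic mean with zero variance may be kept.
4. Restate power for observed parenting as about .78 at ES .12 with 108 per arm, with the SD assumption written out and the .70 and .62 sensitivity values beside it.
5. Reconcile the child age limits in section 5.2 with the Measures table and state an expected teacher response. Only then give power for those sources, by instrument.

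The cost is wording only, in the protocol and in any analysis plan that repeats it; no visit or measure is added. The drawbacks are a slightly lower stated power and an open acknowledgement that these three sources have no immediate post-test.
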